# 1.3 Benefit / Risk Aspects

## Benefits

Subjects will be randomized in a 1:1:1:1 ratio to placebo or one of the three quinagolide doses for four menstrual cycles. This means that 75% of endometriosis patients in the trial will be initially randomized to an active treatment and may benefit from relief of their endometriosis-related pain if the treatment is effective. All subjects in the trial will be provided with rescue analgesics to manage their endometriosis-related pain in case of insufficient pain relief. All subjects included in the trial will also benefit from close and comprehensive monitoring of their conditions.

It should be noted that the treatment and trial-related procedures are provided to the participating subjects free of charge, as Ferring compensates the investigational sites for their expenses.

# Risks

The risks associated with this clinical trial, including the risks of investigational medicinal product (IMP), clinical and laboratory procedures and concomitant medications, are explained to subjects as part of the counselling prior to starting treatment.

# Risks – Investigational Medicinal Product

In the clinical development program for endometriosis, quinagolide has been investigated intravaginally in a total of 111 women in phase 1 trials, of whom 23 were administered tablets at daily doses up to 75  $\mu$ g and 88 were administered vaginal rings at a target release rate of up to 13.5  $\mu$ g/day. In all trials, intravaginal administration of quinagolide was generally safe and well tolerated. The most common treatment-related adverse events with quinagolide vaginal rings (i.e. at a frequency of  $\geq$ 5%, reported by more than 4 subjects) in phase 1 trials were headache, vaginal

discharge, nausea and dizziness. A more detailed description of the safety data from the individual trials is provided in the paragraphs below.

A lower frequency of gastrointestinal adverse events, i.e. nausea and vomiting, was reported following intravaginal administration of quinagolide 75  $\mu$ g tablets once daily for 5 days, compared with oral administration (Trial 000076). The most frequently reported adverse events (i.e. reported by more than 1 subject) following intravaginal administration of quinagolide tablets were headache, dizziness and vaginal discharge. Single administration of quinagolide vaginal ring at a target release rate of quinagolide 4.5  $\mu$ g/day, 9  $\mu$ g/day and 13.5  $\mu$ g/day was locally and systemically well tolerated with the most frequently reported adverse events being headache, vaginal discharge and nausea (Trial 000155). The majority of adverse events occurring in all treatment groups including the placebo group started during the first week of treatment and were considered to be of mild or moderate intensity. No inhibition of ovulation or modification of the menstrual cycle was observed during sequential administration of quinagolide vaginal ring at a target release rate of up to 13.5  $\mu$ g/day (Trial 000207). In addition, quinagolide had no clinically significant effects on clinical chemistry, hematology or urinalysis parameters, nor on vital signs, electrocardiography (ECG) recordings, physical or gynecological examinations in any of the phase 1 trials.

Insertion and/or removal of the vaginal rings may be associated with mild discomfort or spotting, which is expected to be transient. Ring discoloration or breakage at glued junction points could also occur but based on the phase 1 data, there has been no safety concerns associated with these findings. New rings manufactured in a different way (i.e. injection-molded rings instead of glued rings) will be used in the present trial.

Quinagolide is currently marketed outside the United States as an oral tablet formulation for the treatment of hyperprolactinemia. The estimated cumulative exposure of quinagolide until now is more than 280,000 patient years, when administered as an oral tablet in the approved dose range of 25-300  $\mu$ g or higher. The general safety profile of quinagolide is consistent with the class effects of other dopamine agonists, characterized by adverse events involving the gastrointestinal tract and central nervous system. The most frequent adverse drug reactions (all reported as very common, i.e. at a frequency of  $\geq 10\%$ ) in relation to oral administration of quinagolide tablets are nausea, vomiting, headache, dizziness and fatigue. They occur predominantly during the first few days of the initial treatment or, as a mostly transient event, following dosage increase.

A serious but very rare risk associated with quinagolide oral tablets is syncope (<0.01%), which can be resulted from orthostatic hypotension. Orthostatic hypotension occurs at a frequency of 1-10% among patients treated with quinagolide oral tablets. Somnolence rarely (i.e. at a frequency of 0.01% to 0.1%) occurs during treatment with quinagolide oral tablets. Dopamine agonists other than quinagolide have been associated with sudden sleep onset episodes, particularly in patients with Parkinson's disease, and this has resulted in a general warning for the entire class of drugs. In rare cases (i.e. at a frequency of 0.01% to 0.1%), treatment with dopamine agonists has been associated with the occurrence of acute psychosis, which is reversible upon discontinuation. Impulse control disorders involving pathological gambling, increased libido, hypersexuality,

compulsive spending or buying, binge eating and compulsive eating were rarely reported in association with the use of dopamine receptor agonists including quinagolide for the treatment of Parkinson's disease. Ergot-derived dopamine agonists have been associated with an increased risk of fibrosis of the heart valves possibly through activation of 5-hydroxytryptamin 2B receptor (5-HT2B). Quinagolide is a non-ergot-derived dopamine agonist and does not have any 5-HT-receptor activity at clinically relevant doses. Furthermore, no cases of valvular heart disease have been reported with quinagolide.

Quinagolide is not an embryotoxic or teratogenic agent. No adverse effects on embryos or fetuses were observed in the reproductive toxicity studies in rats and rabbits. Based on clinical data for the treatment of hyperprolactinemia, pregnancy outcome data are available for 145 pregnancies in women exposed to quinagolide, with 106 pregnancies leading to live births. Among the 110 liveborn neonates, a total of 5 malformations (4.5%) were reported, which is comparable to the 5-6% malformation rate reported among registered births. In terms of pregnancy loss, 24 (16.6%) spontaneous abortionsb were reported following exposure to quinagolide, which is similar to the 15-16% spontaneous abortion rate reported in the general population. In addition, quinagolide has been investigated for the prevention of ovarian hyperstimulation syndrome (OHSS) in an in vitro fertilization study, in which 85 live births were reported following treatment with oral quinagolide tablets up to 200 µg/day for approximately 20 days without dose titration. Quinagolide did not appear to show any detrimental effects on implantation, pregnancy or live birth rates. In conclusion, exposure to quinagolide during early pregnancy has not been shown to increase the risk of pregnancy losses or congenital malformations compared with a normal pregnant population. Contraception counselling will be offered throughout the trial and condoms will be provided to all subjects at each clinic visit to avoid occurrence of pregnancy during participation of the trial. As a precautionary measure, a urine pregnancy test will be performed at least once per menstrual cycle in the present trial. If the test result is positive and confirmed by a serum  $\beta hCG$  test, the subject will be discontinued from the trial immediately and will be followed up until delivery (see section 8.4).

For further information regarding quinagolide, please refer to the Investigator's Brochure.

# **Risks – Trial Procedures and Concomitant Medications**

The primary endpoint and secondary efficacy endpoints in this trial are patient-reported outcome (PRO) measures that require the subjects' daily assessments of pain intensity, vaginal bleeding pattern, occurrence of sexual intercourse, analgesic use as well as daily and weekly assessments of pain impact, all of which impose no risks to subjects participating in the trial.

A few procedures will be performed at the investigational sites in this trial, i.e. transvaginal ultrasound, blood sampling, ECG, echocardiography, urine pregnancy test and urinalysis, which are either minimally invasive or non-invasive to subjects. The transvaginal ultrasound examinations may be associated with mild discomfort and a very rare risk of infection. The blood sampling might be associated with mild discomfort, bruising and a very rare risk of infection. ECG and

<sup>b Other pregnancy losses included 14 induced abortions (with 1 due to malformation) and 1 ectopic pregnancy.

echocardiography are harmless and painless tests associated with a very rare risk of mild rash where the electrodes are attached. Urine pregnancy tests and urinalysis, simply requiring subjects to urinate, impose no risks to subjects.

All subjects in this trial will be provided with rescue analgesics in the form of ibuprofen 200 mg, which is an approved medicinal product for pain relief and considered generally well-tolerated. The most frequently reported adverse effects with ibuprofen are gastrointestinal in nature and include nausea, vomiting, flatulence and diarrhea. Additional adverse effects may occur at high doses and under long-term treatment. Clinical studies suggest use of ibuprofen, particularly at high doses (2400 mg/day), may be associated with a small increased risk of arterial thrombotic events (e.g. myocardial infarction or stroke). Upper gastrointestinal ulcers, gross bleeding or perforation can occur in approximately 1% of patients treated with ibuprofen for 3-6 months.

If needed, a strong analgesic hydrocodone-acetaminophen may be prescribed by the investigator. The most frequently reported adverse reactions with hydrocodone-acetaminophen are light-headedness, dizziness, sedation, nausea and vomiting. Additional adverse effects may occur at overdose, under long-term treatment and during concomitant intake of alcohol or other drugs. The use of hydrocodone-acetaminophen may also cause mental or physical dependence, opioid addiction, abuse and misuse, which can lead to overdose and death. Serious, life-threatening or fatal respiratory depression may occur with use of hydrocodone-acetaminophen. Acetaminophen has been associated with cases of acute liver failure, at times resulting in liver transplant and death. Most of the cases of liver injury are associated with the use of acetaminophen at doses that exceed 4000 mg per day, and often involve more than one acetaminophen-containing product.

The investigator must assess each subject's risks prior to prescription of hydrocodoneacetaminophen.

#### 2 TRIAL OBJECTIVES AND ENDPOINTS

#### 2.1 Objectives

#### **Primary Objective**

• To evaluate the efficacy of three doses of quinagolide administered as an extended-release vaginal ring compared to placebo on reduction of moderate to severe endometriosis-related pain

#### **Secondary Objectives**

- To evaluate the effect of quinagolide vaginal ring on reduction of endometriosis-related dysmenorrhea, non-menstrual pelvic pain, dyspareunia and analgesic use
- To evaluate the effect of quinagolide vaginal ring on the subject's ability to function
- To evaluate the effect of quinagolide vaginal ring on ovarian function
- To evaluate the effect of quinagolide vaginal ring on endocrine parameters
- To evaluate the effect of quinagolide vaginal ring on vaginal bleeding pattern
- To evaluate the systemic exposure of quinagolide and metabolites after quinagolide vaginal ring administration
- To evaluate the effect of quinagolide vaginal ring on bone turnover markers
- To evaluate the safety profile of quinagolide vaginal ring including adverse events, symptoms of impulse control disorders, ECG and echocardiography findings, routine safety laboratory parameters and ring acceptability
- To validate the newly developed patient reported outcome (PRO) tool: Women's Endometriosis Diary [Note: this objective will be reported separately]

# **Exploratory Objective**

• To explore the effect of quinagolide vaginal ring on endometriosis biomarkers such as angiogenic and inflammatory biomarkers

# 2.2 Endpoints

#### **Primary Endpoint**

• Changes in the mean daily Numerical Rating Scale (NRS) scores for the worst endometriosisrelated pain at cycle 4

#### **Secondary Endpoints**

- Changes in the mean daily NRS scores for the worst endometriosis-related pain on days with menstrual bleeding (i.e. dysmenorrhea) and for the worst endometriosis-related pain on days with no menstrual bleeding (i.e. non-menstrual pelvic pain) at cycle 4
- Changes in the mean daily NRS scores for the worst endometriosis-related pain over 4 menstrual cycles
- Changes in the mean daily NRS scores for the worst dysmenorrhea over 4 menstrual cycles
- Changes in the mean daily NRS scores for the worst non-menstrual pelvic pain over 4 menstrual cycles

Quinagolide, FE 999051	Trial Code: 000165	Date: 29 May 2020
Vaginal Delivery System		E-Study Protocol-20036; Ver.6.0
Clinical Trial Protocol		Supersedes: 5.0
		Page 31 of 130

- Changes in the mean daily NRS scores for the worst dyspareunia on days with sexual intercourse over 4 menstrual cycles
- Frequency of avoiding sexual intercourse due to expected pain over 4 menstrual cycles
- Changes in the mean daily NRS scores for the worst impact of endometriosis-related pain on the subject's ability to function over 4 menstrual cycles
- Changes in the mean weekly scores of the Endometriosis Health Profile-30 (EHP-30) pain impact domain over 4 menstrual cycles
- Changes in vaginal bleeding pattern over 4 menstrual cycles
- Percentage of days with mild and/or strong rescue analgesics used over 4 menstrual cycles
- Total and average doses of mild and/or strong rescue analgesics used over 4 menstrual cycles
- Responder rate assessed as ≥30%, ≥50% and ≥70% reduction from the baseline in mean daily NRS score for the worst endometriosis-related pain, dysmenorrhea and non-menstrual pelvic pain and for the worst endometriosis-related pain impact, over 4 menstrual cycles
- Changes in the mean individual and total symptom and sign severity scores of the Biberoglu and Behrman (B&B) scale at cycle 4
- Changes in the EHP-30 scores over 4 menstrual cycles
- Changes in Patient Global Impression of Severity (PGIS) scores at cycle 4
- Patient Global Impression of Change (PGIC) scores at cycle 4
- Plasma concentration of quinagolide and metabolites during cycles 1 and 4
- Serum levels of mid-luteal phase progesterone at cycle 4
- Proportion of subjects with serum levels of mid-luteal progesterone ≥25 nmol/L (7.9 ng/mL) at cycle 4
- Serum levels of mid-luteal estradiol, prolactin, thyroid-stimulating hormone (TSH) and insulinlike growth factor-1 (IGF-1) at cycle 4
- Changes in bone turnover markers, determined by bone resorption marker serum C-terminal cross-linking telopeptide of type 1 collagen (s-CTx) and bone formation marker serum procollagen type I N propeptide (s-PINP) at cycle 4
- Changes in ECG parameters including PR interval, QT interval, corrected QT using Fridericia's formula (QTcF) and QRS interval at cycle 4
- Proportion of subjects with abnormal clinically significant echocardiography findings indicating valvular heart disease at cycle 4
- Proportion of subjects identified with potential impulse control disorders by the questionnaire for impulsive-compulsive disorders at cycle 4
- Frequency and intensity of adverse events
- Changes in circulating levels of clinical chemistry and hematology parameters, urinalysis parameters, and proportion of subjects with markedly abnormal changes
- Frequency and intensity of ring acceptability parameters over 4 menstrual cycles

# **Exploratory Endpoint**

• Changes in endometriosis biomarkers such as serum levels of VEGF, placenta growth factor (PIGF), interleukin 6 (IL-6) and soluble fms-like tyrosine kinase 1 (sFlt-1) at cycle 4

#### **3** INVESTIGATIONAL PLAN

#### 3.1 Overall Trial Design

#### 3.1.1 Trial Design Diagram

Screening					Treatment						Follow-up		
							Placebo vaginal r	ing for 4 cycl	les				
	Run-in period of 2 menstrual cycles a				OVR dose load 360 µg for 4 cycles								
					QVR dose load 720 μg for 4 cycles								
					QVR dose load 1080 μg for 4 cycles								
-	TVU	LH surge Endocrine							LH	surge Endocrine	TVU		
			BTM Biomarkers b		PK	PK			PK	BTM Biomarkers b	РК		
			ECG d Echo d		PK PG °	Υĸ			IK	PK	ECG		
			Leno	QICD EHP-3		EHP-30	EHP	-30	EHP-30		Echo d QICD EHP-30		
		PGIS		PGIS	_			-50	2.11 30		PGIC		
C-SSR	LS			Ring C		Ring Qs	Ring C-SS		Ring Qs		Ring Qs C-SSRS		
	Vaginal bleeding Analgesic use											Vaginal b Analges	-
e-Diary	Sexual intercourse Pain impact e											Sexual into	
	NRS RS(Run-in) f			B&B							B&B		NRS
line l	KS(Kun-in)												
Washout Run-in		RM	TH	RM	PK	- RM	RN		RM	Ē	En		- En
KM+7 % Visit Run-in Informed cons		(+7 g/	LH+7 g / Visit 3	[+7 º/ \ ndomis	Visit s	RM+7 g / Visit 6	  +7  /		[+7 º/	LH+7 g / Visit 9	[+7 g / y d-of-tr		[+7 g / y d-of-tr
KM+/ */ V1SII 1 Run-in Informed consent	7	RM+7 g /Visit 2	Visit 3	RM+7 g / Visit 4 Randomisation	PK Visit g / Visit 5	Visit 6	RM+7 s / Visit 7		RM+7 g / Visit 8	Visit 9	RM+7 g / Visit 10 End-of-treatment		RM+7 g / Visit 11 End-of-trial
Ŧ	Cycle -2		Cycle -1		Cycle 1		Cycle 2	Cycle	3	Cycle 4	a -	Cycle 5	

Abbreviations: B&B=Biberoglu and Behrman Scale, BTM=bone turnover markers, C-SSRS=Columbia Suicide Severity Rating Scale, Echo=echocardiography, ECG=electrocardiography, EHP-30=Endometriosis Health Profile-30 Questionnaire, LH=luteinizing hormone, LH+7=7 days after LH surge, NRS=Numerical Rating Scale, PGIC=Patient Global Impression of Change, PGIS=Patient Global Impression of Severity, PG=pharmacogenetic(s), PK=pharmacokinetic(s), QICD=questionnaire for impulsive-compulsive disorders, QVR=quinagolide vaginal ring, Ring Qs=ring acceptability questions, RM=return of menses, RM+7=day 7 of return of menses, TVU=transvaginal ultrasound

- a In case of technical issues at the start of the run-in period, subjects are allowed to re-start cycle -2. Subjects that screen fail due to the temporary trial hold during the coronavirus disease 2019 (COVID-19) pandemic may be re-screened.
- b Blood samples for potential endometriosis biomarkers will be collected for all subjects. If subjects provide a separate informed consent,
- additional blood samples for potential analyses of circulating cell-free DNA and microRNA will also be collected. c If subjects provide a separate informed consent, a blood sample for pharmacogenetic analysis will be collected.
- d ECG and Echo at screening can be arranged anytime during cycle -1 (e.g. at visit 3) but results must be available before randomization. ECG and Echo at cycle 4 can be performed within ±2 weeks of visit 10.
- e Pain impact will be assessed on both a daily and a weekly basis.
- f Scoring of the worst endometriosis-related pain during the past menstrual cycle on the NRS will be performed on paper at the run-in visit. Daily scoring of endometriosis-related pain on the NRS is captured by e-Diary.
- g Visits on RM+7 or LH+7 can be scheduled RM+6-10 or LH+6-9, i.e. day 6 to day 10 of return of menses or 6-9 days after LH surge, respectively. PK visit (visit 5) can be arranged within 1-5 days of randomization (visit 4).

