Three phase 1 trials have been conducted in Germany and the United Kingdom with intravaginal administration of quinagolide in healthy volunteers. Intravaginal administration of quinagolide tablets has been shown to be associated with higher bioavailability than oral administration due to reduced first pass metabolism in a single and multiple ascending dose trial comparing intravaginal and oral administration (Trial 000076). Following single administration of quinagolide vaginal ring at a target release rate of quinagolide 4.5  $\mu$ g/day, 9  $\mu$ g/day or 13.5  $\mu$ g/day a, Tmax was reached at 36-48 hours for all three doses and plasma concentration slowly declined over time for up to 35 days (Trial 000155). Furthermore, no dose accumulation and no impact on ovarian function or menstrual cyclicity were observed following sequential administration of quinagolide vaginal rings for two menstrual cycles (Trial 000207).

<sup>a The three strengths of quinagolide vaginal ring investigated in phase 1 trials are expressed in the content of quinagolide hydrochloride instead of quinagolide. The exact quantities of drug substance are minimally adjusted for the present trial due to a minor change in ring manufacturing. Quinagolide vaginal rings in phase 1 trials contain a dose load of quinagolide hydrochloride 400 µg, 800 µg and 1200 µg corresponding to a target release rate of quinagolide hydrochloride 5 µg/day, 10 µg/day and 15 µg/day, respectively, which are equivalent to a target release rate of quinagolide 4.5 µg/day, 9 µg/day and 13.5 µg/day.

Quinagolide, FE 999051 Vaginal Delivery System Clinical Trial Protocol

Vaginal ring administration of quinagolide avoids repeated rapid daily rises of quinagolide levels as seen with oral administration and thereby has improved tolerability of quinagolide based on safety evaluations in phase 1 trials. In addition, an extended-release formulation with replacement of the vaginal ring every menstrual cycle is more suitable for the long-term management of endometriosis than a daily formulation.

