# 6.4.6 Visit 10 (End-of-Treatment / RM+7 of Cycle 4)

If subjects attend all scheduled visits and complete the treatment, an end-of-treatment visit (visit 10) will be scheduled on RM+6-10 of cycle 4. If subjects are discontinued from the treatment prematurely, an end-of-treatment visit with the following end-of-treatment assessments should be scheduled as soon as possible (preferably within 7 days of the last ring removal).

The following must take place first:

- Ensure the completion of the EHP-30 questionnaire by the subject
- Ensure the completion of the PGIS scale by the subject

- Ensure the completion of the PGIC scale by the subject
- Completing the first part of B&B scale based on the subject's verbal response
- Completing the questionnaire for impulsive-compulsive disorders (QICD) based on the subject's verbal responses
- Ensure the completion of the eC-SSRS by the subject

Once the above has been completed, the following must be performed:

- Vital signs [note: vital signs must be performed before blood sampling]
- ECG [*note*: this can be done within ±2 weeks of the visit and must be performed before blood sampling when applicable]
- Echocardiography [*note*: this can be done within ±2 weeks of the visit]
- Physical examination
- Gynecological examination
- Transvaginal ultrasound
- Investigator completing the second part of B&B scale based on findings from an examination of pelvic tenderness and induration (see section 7.2.2.1)
- Urine pregnancy test [*note*: this is performed prior to ring insertion / removal. Results must be negative. If positive, a serum test must be done]
- Urinalysis
- Blood collection for analysis of:
  - Plasma concentration of quinagolide and metabolites [*note*: this is performed prior to ring insertion / removal]
  - Clinical chemistry and hematology parameters
- Removal of the used ring. Supervision by the site staff can be provided if needed
- Ensure the completion of the ring acceptability questionnaire (full version) by the subject

Lastly, the following must take place at this visit:

- e-Diary review
- Confirmation of the start date and, if applicable, stop date of menses in the current cycle
- Drug accountability of the ring and ibuprofen as applicable
- Recording of use of any concomitant medications
- Recording of adverse events
- Completion the end-of-treatment question where subjects will be asked which treatment (placebo or quinagolide) they believe they have received

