## 7.2.2.8 Electrocardiography (ECG)

The 12-lead ECG will be recorded within cycle -1 and at cycle 4 (around visits 3 and 10). ECG at screening can be performed anytime during cycle -1, e.g. at LH+7 visit (visit 3) but results must be available before randomization. The report must be reviewed, signed and dated by the investigator before randomization. Results at randomization will be used as baseline. ECG at cycle 4 can be performed within  $\pm 2$  weeks of visit 10. ECG will be recorded with a calibrated ECG device after the subject has been in supine position for at least 5 minutes. ECG must be performed before blood sampling when applicable.

The parameters to be assessed are heart rate, PR interval, RR interval, QRS interval, QT interval and QTcF interval (i.e. QT correction according to the Fridericia's formula  $QTcF=QT/RR^{0.33}$ ). ECG recordings will capture at least four QRS complexes, i.e. 3 evaluable RR intervals. All ECG recordings will be sent to a central cardiac laboratory for evaluation as normal or abnormal. If the results of central reading are abnormal, the investigator will evaluate whether the abnormal finding is clinically significant or not. Any occurrence of de- or re-polarization disorders (QT prolongation), arrhythmic disorders or other abnormalities will be assessed in comparison to the baseline.

ECG may be repeated for quality reasons and in this case the repeated assessment will be used for analysis. If subject demonstrates a prolongation of QTc interval  $\geq$ 500 msec or a QTc interval change from baseline  $\geq$ 60 msec, two additional ECG assessments should be acquired 2-5 minutes apart and all three ECG assessments should be re-evaluated by the central cardiac laboratory. If the averaged values from three consecutive ECG assessments indicate a prolongation of QTcF interval  $\geq$ 500 msec or a QTcF interval change from baseline  $\geq$ 60 msec as confirmed by the central cardiac laboratory, the subject should be discontinued from the treatment (see section 3.6.7).

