ECG and echocardiography will be performed to monitor cardiovascular safety. ECG will be assessed prior to randomization during cycle -1, at cycles 4 and 8 (prior to or at visit 4, at visits 11 and 16). ECG must be performed after vital signs but before blood sampling as applicable. ECG and echocardiography at screening can be arranged anytime during cycle -1, e.g. at LH+7 visit but results must be available prior to randomization.

Echocardiography at cycles 4 and 8 can be performed within ± 2 weeks of end-of-cycle 4 visit and end-of-cycle 8 visit, respectively.

A modified questionnaire for impulsive-compulsive disorders will be completed electronically by trained trial coordinators based on subjects' verbal response prior to randomization at cycle -1, at cycles 4 and 8.

A urine pregnancy test will be performed at each clinic visit (except for the PK visit during cycle 1) throughout the trial. If the test result is positive and is confirmed by a following serum β hCG test, the subject should be discontinued from the trial. Urinalysis is performed at the run-in visit, at cycles 4 and 8.

The self-assessments of NRS, occurrence of sexual intercourse, the impact of pain, vaginal bleeding and analgesics use will be done by the subjects in the e-Diary. The daily e-Diary should be completed by the subjects before bedtime every night throughout the trial that is from visit 1 until the end-of-trial visit. Additional assessments of pain impact will be done in the weekly e-Diary. The weekly e-Diary should be completed at the end of each week throughout the trial that is from visit 1 to end-of-trial visit.

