10.4.2.1 Summary Statistics

Descriptive statistics, i.e., the number of subjects with data, mean (standard deviation), median, minimum, and maximum values, will be presented for observed values and change from baseline at each time-point for each ECG variable.

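### The cycle 4 ECG window in protocol version 6.0 runs past removal of the last ring, and the SAP pools ring-in and ring-out readings in one change from baseline

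*Protocol*

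**What the plan says.** The protocol lists as a secondary endpoint: "Changes in ECG parameters including PR interval, QT interval, corrected QT using Fridericia's formula (QTcF) and QRS interval at cycle 4". Section 7.2.2.8 schedules two ECGs, one in cycle -1 and one at cycle 4, so a single scheduled post-baseline reading carries the endpoint.

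The timing allowance for that reading is the same throughout version 6.0. Section 3.1.1 footnote d states: "ECG and Echo at cycle 4 can be performed within ±2 weeks of visit 10". Section 3.1.2, the footnotes to Table 6-1 and section 7.2.2.8 agree. The visit 10 list in section 6.4.6 adds an order: "this can be done within ±2 weeks of the visit and must be performed before blood sampling when applicable". Further down the same list comes: "Removal of the used ring. Supervision by the site staff can be provided if needed". No ring is inserted after that. Section 3.1.2 describes cycle 5 as post-treatment follow-up, and SAP section 1 confirms that version 6.0 has no Part B.

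For women who stop early, protocol sections 6.1.1 and 6.4.6 ask for an end-of-treatment visit, preferably within 7 days of the last ring removal.

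The SAP describes the eight-cycle design. Its section 3 places the ECG at visits 11 and 16, says that "ECG must be performed after vital signs but before blood sampling as applicable", and gives the ±2 weeks to echocardiography only. In SAP 10.4.2.1, descriptive statistics "will be presented for observed values and change from baseline at each time-point for each ECG variable".

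**The concern.** The ECG endpoint is there to describe cardiovascular risk under treatment (protocol 3.6.2). A conduction or repolarization effect that depends on the circulating drug level can be seen only while drug is present. Version 6.0 gives the ECG and the echocardiogram the same window. For echocardiography this matters less, because a structural valve change need not depend on the ring being in place.

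The last ring leaves at visit 10, so the later half of the window lies after treatment. If some women have their only scheduled post-baseline ECG then, and the SAP averages those readings with ring-in readings, the active arms look closer to no change than they were on treatment. For a safety endpoint that is the unfavourable direction.

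There is also a tension within the protocol. Sections 3.6.7 and 7.2.2.8 make a confirmed QTcF finding a criterion for stopping treatment, yet the only scheduled post-baseline ECG may take place when treatment has already ended.

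**Working it through.** The plan states no figure for this point, so there is none to reproduce. The check sets the timing and data-handling rules side by side.

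**1. Window against ring removal (version 6.0 completer).** Visit 10 is day 0.
- Permitted window: day -14 to day +14, which is 28 days.
- Ring in place: day -14 up to removal on day 0.
- Ring out: after removal on day 0 up to day +14, which is 14/28 = 50% of the permitted days. This is a share of the calendar allowance, not of the readings.

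**2. Which readings fall where.**
- ECG at visit 10 in the listed order: ring in. The ECG precedes blood sampling, the drug-level sample precedes ring removal, and removal comes later in the list.
- ECG on an earlier day in the window: ring in.
- ECG on a later day: ring out. The rule about blood sampling binds only when applicable, so it does not prevent this.
- ECG of an early discontinuer: ring out whenever the end-of-treatment visit follows removal. The preferred limit is 7 days. If the ±2 weeks is read as applying to that visit too, the reading could come 7 + 14 = 21 days after removal.

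**3. What the SAP does with them.** SAP 10.3 (laboratory) and 10.4.1 (vital signs) limit treatment-emergent data to the time of residual drug effect. SAP 10.4.2 to 10.4.2.2 (ECG) contain no such limit, no analysis window and no ring-status rule. All cycle 4 readings therefore enter one summary.

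**4. Effect of pooling.** Let D be the mean effect with the ring in, f the share of an arm's readings taken ring-out, and r the fraction of the effect still present in those readings. The expected arm mean effect is

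D × [(1 - f) + f × r].

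With r = 0 this is D × (1 - f). For a purely illustrative D of 10 ms, it gives 9.0, 7.5 and 5.0 ms at f = 10%, 25% and 50%. Neither D nor f is in the documents. In principle f can lie anywhere from 0 to 100%.

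**5. Why no value of r is offered.** The documents give no half-life after ring removal. Protocol 3.6.4 gives oral 75 µg tablet values: mean peak 8 pg/mL at about 1 h, trough 0.8 pg/mL, AUC over the dosing interval 42.3 h·pg/mL. A single-exponential decline from 8 to 0.8 pg/mL over 23 h has rate ln(10)/23 = 0.100 per h. The area after the peak alone would then be (8 - 0.8)/0.100 = about 72 h·pg/mL. That exceeds the stated 42.3, so the decline is not a single exponential and a half-life read from these two points cannot be used. The vaginal tablet values (13 to 7 pg/mL) include continuing absorption. Residual drug after removal is therefore left unquantified.

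**The case against.** The other side has a good deal to say.

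- **The default is ring-in.** The ECG is a visit 10 procedure, and the listed order puts it before removal. The ±2 weeks is an allowance, and readings may well cluster at the visit. This stands. A reader might infer from the 50% of permitted days that about half the readings are off drug, or that an effect is halved. That needs dates spread evenly over the window, which the documents do not support.
- **Ring-out is not the same as drug-free.** No half-life is given, and protocol 3.6.2 mentions active metabolites, sometimes at high levels. This stands. The documents establish ring status, not plasma level.
- **It is not the only ECG.** A cycle -1 ECG is taken, and repeats are allowed for quality or after a QTc flag. This is correct. The claim is limited to the only scheduled post-baseline ECG.
- **Little depends on it here.** Protocol Table 9-2 and the SAP treat ECG descriptively, no statistical analysis is performed after early termination, most women were randomized under version 5.0, and protocol 1.3 reports no clinically significant ECG effect in phase 1. This limits the impact but does not supply the missing rule.
- **The SAP's tighter ECG text is not a contradiction.** It describes the eight-cycle design, in which women continuing into Part B had a new ring in after the cycle 4 visit. This is accepted. The difference between the documents is not counted as an error.
- **The data allow recovery.** Removal date and time are recorded (protocol 7.4.18) and listed (SAP 8.1.3). This is true, and it is what makes the remedy cheap.

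**Conclusion.** The point holds in a limited form. Version 6.0 permits the only scheduled post-baseline ECG after the last ring has been removed, early discontinuers add further ring-out readings, and SAP 10.4.2.1 pools everything into one cycle 4 change from baseline. Any level-dependent PR or QTcF effect would be diluted in proportion to the ring-out share, provided that the effect fades once the ring is out.

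The size cannot be stated, because neither the share nor the residual drug level is in the documents. The readings at issue are those of version 6.0 completers who used the later part of the window and of early discontinuers; their number is not given. The documents do not show that the QTcF endpoint was in fact measured off drug. They show that nothing in the plan would reveal it if it was. This is a worthwhile, inexpensive improvement and does not invalidate the safety evaluation.

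**What to change.** **SAP 10.4.2.1.** Compare each ECG date with the recorded ring-removal dates.
- Base the cycle 4 change on readings taken on or before the last ring removal.
- For women who went on to Part B, readings with a ring in place also count. Check the arm label, because SAP section 3 moves Part A placebo women to an active ring for Part B, so a reading after that switch is not a placebo reading.
- Show post-removal readings separately, including those of early discontinuers, with days since removal.
- Where ECG and removal fall on the same day and their order is not recorded, state which group the reading joins.

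**Protocol, for any reuse of the design.** In 3.1.1 footnote d, 3.1.2, 6.4.6 and 7.2.2.8 (and the matching Table 6-1 footnote), separate the ECG window from the echocardiography window so that the cycle 4 ECG of completers is an on-treatment reading. Reconcile the ECG timing with the QTcF treatment-discontinuation criterion in 3.6.7 and 7.2.2.8; how to do so is for the sponsor's clinical team.

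**Cost.** The SAP change is one date comparison on data already collected, with somewhat fewer ECGs in the on-treatment summary. The protocol change narrows the scheduling window, and a completer who misses it would have no on-treatment reading. Neither change addresses the fact that a cycle 4 ECG comes late in the life of the ring, after the early concentration peak.
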